Official title: The Antibacterial Effect of Nanosilver Fluoride in Relation to Caries Activity in Primary Teeth: a Randomized Controlled Clinical Trial

NCT number: NCT05221749

Date uploaded: 25th July, 2023

**THE ANTIBACTERIAL EFFECT OF NANOSILVER
FLUORIDE IN RELATION TO CARIES ACTIVITY IN
PRIMARY TEETH:
A RANDOMIZED CONTROLLED CLINICAL TRIAL**

2021/2022

ABSTRACT

Background: Dental caries is among the most prevalent chronic diseases in children. Minimally invasive dentistry is a highly convenient and efficient method of managing caries in pediatric patients. Recently, Nanosilver fluoride (NSF) has emerged as a promising topical fluoride agent with a potent cariostatic and antibacterial potential. This new anticaries agent is used as an alternative to overcome the drawbacks of topical fluoride and silver diamine fluoride (SDF) in caries prevention.

Objective: To assess the antibacterial effect of NSF in relation to caries activity in dentin caries lesions of primary teeth in comparison to SDF after 1 month.

Methods: Fifty children aged 4 to 6 years old with active dentin caries lesions according to ICDAS score 5 will be recruited from the Pediatric Dentistry clinic at the Faculty of Dentistry, Alexandria University. The children will be equally and randomly allocated into 2 groups; the first group will be treated using NSF, while the second group will be the control group receiving SDF treatment. Microbiological assessment using a microbrush will be done at baseline and follow-up appointments to record the bacterial counts using the suitable culture media, the results will be expressed in colony forming units (CFU). Data regarding the children's oral health will be collected and their dmf index will be scored. The arrest of active carious lesions will be measured after 1 month according to ICDAS criteria and a microbiological assessment will be completed.

Results: The relation between bacterial counts (CFU) and lesion activity for both interventions will be assessed. The data collected will be statistically evaluated with the suitable tests and tabulated.

Keywords: Nanosilver fluoride, silver diamine fluoride, antibacterial, caries arrest, microbiology, primary teeth, pediatric, clinical trial

INTRODUCTION

Dental caries is a chronic disease, ranking among the most highly prevalent diseases in children. According to the Global Burden of Disease study in 2017,¹ untreated dental caries in the deciduous dentition was the 10th most prevalent condition globally, affecting 532 million children worldwide.² It is one of the most common infectious diseases of childhood which is evident from the fact that in children, it is 7 times more common than hay fever or allergic rhinitis and 5 times more common than asthma.³ Under severe conditions, the pain and discomfort associated with dental caries can affect the quality of life of children and may lead to acute and chronic infections, changed eating and sleeping habits, and an increased risk of hospitalization.^{4,5}

Among a variety of chemotherapeutic agents that have been tested for preventing and arresting caries. Silver diamine fluoride (SDF) has a proven antibacterial action⁶ and releases fluoride ions onto the applied tooth surfaces, therefore, assisting in enamel remineralization⁷. Recently, the promising results of published clinical trials have popularized the use of SDF throughout the world.^{8,9} Today, it is available for arresting caries as a simple, non-invasive, low-cost medication.^{8,10} The major drawback of SDF is the staining of carious tissue to dark black due to the oxidation of the ionic silver in its formulation, along with reversible slightly painful lesions in oral mucosa caused by accidental contact of the SDF solution with soft tissues, these lesions usually disappear within 48 hours.¹¹

New formulations of silver nanoparticles (AgNP) show potent antimicrobial properties against a wide variety of microorganisms.¹²⁻¹⁴ Haghgoo et al.¹⁵ suggested the incorporation of nanosilver in varnishes and reported increased antimicrobial properties against cariogenic microorganisms such as *streptococcus mutans* and *streptococcus salivarius*. Nanosilver fluoride (NSF) is an experimental formula obtainable as a yellow solution containing uniformly dispersed silver

nanoparticles and fluoride. It was developed to be an effective anti-caries agent that does not stain the porous dental tissues black as does SDF.¹⁶

Interestingly, it is unknown if the reduction in caries activity brought about the use of nanosilver fluoride is due to its remineralizing action, antibacterial action, or due to a combination of both.^{17,18} There is a need to understand the interaction of topical caries arresting agents like NSF and SDF with the oral microbiome associated with dental caries, since the in vitro findings cannot be extrapolated to the clinical use of NSF.¹⁹

To our knowledge, no publication has reported the in vivo antimicrobial efficiency of NSF on the primary dentition in comparison to SDF. Therefore, this study will be undertaken to evaluate and compare the clinical antibacterial and cariostatic effectiveness of NSF compared to that of SDF in 4-6 year old children. The null hypothesis of this study is that no statistically significant difference will be detected regarding the antibacterial effect of nanosilver fluoride in relation to caries activity in dentin caries lesions of primary teeth, in comparison to silver diamine fluoride, after one month.

AIM OF THE STUDY

General aim

To assess the antibacterial effect of nanosilver fluoride in relation to caries activity in dentin caries lesions of primary teeth in comparison to silver diamine fluoride after one month.

Specific aims

- To compare the change in *Streptococcus mutans* and *Lactobacilli* counts in dentin caries lesions of primary teeth after one month of the application of nanosilver fluoride or silver diamine fluoride.
- To compare the effect of nanosilver fluoride to that of silver diamine fluoride on caries lesion activity in dentin caries lesions of primary teeth after one month of application according to ICDAS criteria.

MATERIALS AND METHODS

Study Design

This will be a randomized, parallel, two-arm clinical trial, with a 1:1 allocation ratio. It will be set up and reported according to the CONSORT guidelines.²⁰

The PICOT question is: will children (4-6 years old) with an active carious lesion (ICDAS code 5) (population; P) using nanosilver fluoride varnish (Intervention; I) in comparison to silver diamine fluoride (comparison; C) show a greater percentage decrease in bacterial counts in the caries lesion (outcome; O) after 1 month follow-up (time; T)?

Study Setting and Location

The study will take place in the Department of Pediatric Dentistry and Dental Public Health at the Faculty of Dentistry and the Department of Medical Microbiology and Immunology at the Faculty of Medicine, Alexandria University, Alexandria, Egypt.

Sample

Sample size estimation

The minimum sample size was calculated based on the results of a previous study.⁶ Adopting a power of 80% and a statistical significance level of 5% ($\alpha=0.05$), 24 children in each group will be needed to generate a statistically significant result. The sample size will be increased to 25 children of both genders per group to compensate for possible drop-out participants. Total sample size= $25 \times 2 = 50$. The sample size estimation was based on Rosner's method²¹ and calculated using G*Power 3.1.9.7.²²

Eligibility criteria

The participants enrolled in this study will be selected after fulfilling the following criteria:

Inclusion Criteria

- Children aged 4-6 years old.
- The presence of at least one active carious lesion on a primary tooth, with a score of 5 according to the International Detection and Assessment System (ICDAS), detected by visual-tactile inspection to assess lesion severity and activity.²³ (Appendix I, Tables 1 and 2)
- Completion of an informed consent to participate in the study.

Exclusion criteria

- Children reporting spontaneous or elicited pain from caries or showing any signs of pulpal infection, swelling, abscess, obvious discoloration of the tooth, or premature mobility.¹¹
- Reported usage of local or systemic antibiotics, chlorhexidine or fluoride mouthwashes within the last 2 weeks.²⁴
- Children presenting with special health care needs or undergoing medical treatment for chronic or acute diseases affecting salivary flow.
- Allergy or sensitivity to silver or any of the materials included in the study.¹¹
- Child weight less than 10 Kg (to avoid concerns for toxicity).²⁵

Randomization technique and allocation²⁶

Subjects complying with the inclusion criteria will be randomly assigned using a computer-generated list of random numbers to either the NSF or the SDF group (www.random.org). Allocation will be performed by a trial independent individual and the allocation ratio is intended to be equal (1:1).

Allocation concealment²⁷

An assistant will be responsible for giving each participant a serial number that will be used for his/her allocation. A duplicate of this number will be kept in an opaque envelope indicating to which group the patient belongs. This envelope will be kept by a trial independent individual who will be assigned the role of opening it only at the time of intervention; so that the group to which the child is allocated is concealed from the investigator.

Grouping

Participants will be randomly and equally allocated to one of the two treatment groups:

- **Test group (NSF):** Twenty-five children meeting the eligibility criteria will receive Nanosilver fluoride.
- **Control group (SDF):** Twenty-five children meeting the eligibility criteria will receive 38% Silver diamine fluoride.

Blinding

The investigator will not be blinded to the treatment type as the SDF solution has a bluish tint and will stain the active caries lesions black, while the NSF solution has a yellowish tint and is not expected to stain the lesions. However, the participants, the statistician, and the microbiologist will be blinded to the treatment group.

Materials

PEG-coated nanosilver fluoride (50 nm average particle size) will be prepared in the Center of Excellence for Research in Regenerative Medicine and its Applications (CERRMA) at the Faculty of Medicine, Alexandria University).

Once all of the above characterization tests and cytotoxicity assays yield satisfactory results, fluoride will then be added. Ten ml of 22,600 ppm of 5% Sodium fluoride varnish will be added to the nanosilver particles in a light proof brown bottle, vigorous stirring will be performed to achieve uniform dispersion of the nanosilver particles.

- 38% silver diamine fluoride: Advantage Arrest, Elevate Oral care (8 mL bottle).*²⁸
- Gauze
- Mirror
- Cotton rolls and pellets
- Tweezers
- Ball ended probe
- Plastic dappen dish
- Petroleum jelly
- Microbrush

Materials for the microbiological assessment

- Microbrush
- Mitis Salivarius Bacitracin (MSB) agar (selective culture media for *S. mutans*), prepared according to the manufacturer's instructions.**
- Rogosa SL agar plates (selective culture media for *lactobacilli*), prepared according to the manufacturer's instructions.***

- Saline as a transport medium.
- Sterile test tubes.
- Sterile plastic Petri dishes.
- Anaerobic gas jar.
- Incubator. ***

* Elevate Oral Care, LLC, West Palm Beach, FL, USA.

** Difco Laboratories Inc, NJ, USA.

*** Himedia Laboratories, Mumbai, India.

****Red line by binder

Method

First visit: baseline examination

After obtaining the informed consent from the care giver/parent, the researcher will provide oral hygiene instructions to each of the study participants and will inform them about the importance of maintaining good oral hygiene and a proper diet.²⁹ The patients and caregivers will be informed about the therapeutic intervention to be applied, the possible outcomes, and side effects in detail. All of the examinations and interventions will be done by one calibrated examiner. All of the lesions in the children's oral cavity indicated for treatment with NSF or SDF will be treated and sampled for microbiological analysis.³⁰

On the day of the intervention, the children will be asked to refrain from tooth brushing in the morning, as well as eating and drinking (except water) for at least two hours before the appointment. The dmf index will be recorded for each patient.

For caries treatment in all groups, no caries or unsupported enamel will be removed. The patients will be instructed to rinse with a cup of water, then any gross debris will be gently removed with a piece of gauze. The tooth will then be partially isolated using cotton rolls and a saliva ejector. Additionally, petroleum jelly will be applied to the gingiva for added protection. Before applying the intervention, a 2-mm wide microbrush will be rubbed on the carious lesion for 4 seconds to collect the baseline microbiological sample.⁶ The microbrush will then be inserted in a sterile test tube containing 1 mL of saline and transported to the microbiology laboratory within 1-2 hours.³¹

Intervention

Test group (NSF):

- 1 drop of NSF will be dispensed into a sterile plastic dappen dish.

- Affected tooth surfaces will be dried with a gentle flow of air.
- The solution will be applied to the carious lesions using a microbrush.
- No more than one drop of NSF will be used for each patient.
- The NSF solution will be left in contact with the tooth surface for 1 minute.³²
- Any excess will be removed with a cotton pellet to minimize systemic absorption.

Control group (SDF):

It will be applied according to the manufacturer's instructions and the AAPD guidelines for using SDF.^{28,30}

- One drop of 38% SDF will be dispensed into a sterile plastic dappen dish.
- Affected tooth surfaces will be dried with a gentle flow of air.
- A microbrush will be dipped into the SDF and dabbed on the side of the dappen dish to remove excess liquid before applying the solution to only the affected tooth surface.
- No more than one drop of SDF will be used for each patient.
- The SDF will be allowed to dry on the lesion for 1 minute.³³
- Any excess will be removed with a cotton pellet to minimize systemic absorption.

After the application of fluoride agents, all of the children will be instructed not to drink or eat for 1 hour after the appointment, their parents will be asked to observe this instruction.²⁴ Additionally, for ethical considerations, teeth not treated with SDF or NSF or those showing signs of failure or any new carious lesions that will appear during follow-up period will be appropriately treated.

Microbiological Procedure

1. Sample dilution

All samples will be dispersed by vortexing for 30 seconds then 10-fold serially diluted using sterile saline. A measure of the dilution will then be used for traditional plate culturing methods.^{34,35}

2. Culture

Aliquots of 10 ml of each dilution will be inoculated into freshly prepared Mitis Salivarius agar and Rogosa agar media respectively, using a micropipette.

- Mitis Salivarius agar plates will be incubated anaerobically in an atmosphere containing 10% CO₂ at 37°C for 72 hours to detect *Streptococcus mutans* counts.
- Rogosa agar plates will be incubated aerobically at 37° C for 48 hours to detect *Lactobacilli* count.

3. Isolation and Enumeration

Following the predetermined incubation period, colonies grown on the specified media will be counted and represented as (CFU/ml). *Streptococcus mutans* will be identified based on their characteristic morphology on Mitis Salivarius agar plates. Similarly, *Lactobacilli* will be identified biochemically and microscopically on the basis of their morphology.

4. Colony count

The number of colonies will be determined and expressed as colony forming units using the following equation.³⁶

$$\text{CFU/ml} = \frac{\text{n}^{\circ} \text{ of colonies} \times \text{dilution factor}}{\text{Volume taken in ml (1)}}$$

STUDY OUTCOME

Treatment effect will be evaluated after one month by comparing:

- Microbiological assessment of colony forming units (CFU) of *Streptococcus mutans* and *Lactobacilli*.
- Caries activity according to ICDAS criteria.

Follow up

All patients will be recalled after one month. On the day of the recall appointment, patient preparation will be done as mentioned before.

Outcome assessment

- Microbiological assessment will be done as mentioned before and CFU counts will be recorded.
- Lesion activity will be assessed according to the ICDAS criteria. Using a blunt ended probe, if the cavity is found to be shiny and feels hard on gentle probing of the dentin, it will be recorded as an inactive lesion. While if it remains soft or leathery on gentle probing, it will be recorded as an active lesion.

STUDY PLAN

[figure not shown]

Figure: flow chart of the study plan

STATISTICAL ANALYSIS

The statistical software SPSS version 27.0 for Windows will be used for data analysis. The outcome variable is the number of colony forming units (CFU) of *streptococcus mutans and lactobacilli*, and the number of arrested caries lesions after 1 month in both the SDF and NSF groups. The collected data will be recorded and statistically evaluated.

The Chi square test will be used to compare the difference between the two groups regarding change caries lesion activity, the T-test or the Mann-Whitney U test will be used to analyze the differences between the microbiological samples, Wilcoxon signed rank will be used to assess the changes over time in bacterial counts. Regression analysis will be used to assess the potential confounders such as gender, social status, and dietary habits. The data will be graphically presented with suitable graphs. The level of statistical significance will be set at 5%.

ETHICAL CONSIDERATIONS IN SUBJECTS INVOLVING HUMAN SUBJECTS

1. This research protocol will be approved by the Research Ethics Committee of Alexandria University Faculty of Dentistry (IORG 0008839-IRB No. 0359-12/2021). prior to any research-related activities.
2. All research activities involving human subjects will abide by the Declaration of Helsinki³⁷ and other ethical guidelines adopted by the Research Ethics Committee of Alexandria University Faculty of Dentistry.
3. Benefits:
 - It will provide a caries arresting treatment for young children with multiple active carious lesions using minimally invasive atraumatic procedures.
 - It will allow overcoming the disadvantages of silver diamine fluoride including black staining of the teeth and any clothes it contacts, soft tissue injury, unpleasant taste for children.
 - Support the use of nanosilver fluoride as a more convenient and more economical substitute to silver diamine fluoride for caries arrest in the primary dentition.
4. Harms/Risks:

Nothing more than the standard of care and the risk of black discoloration with SDF treatment.
5. Privacy and confidentiality:

Each participant will be provided with a serial number that will only be accessible to the principal investigator. No data regarding the identity of the participants will be shared under any circumstances. All participants or their guardians must provide a written informed consent prior to any procedures.

DURATION OF THE STUDY

Study Activity	Month								
	1	2	3	4	5	6	7	8	9
Purchase material	✓	✓							
Patient recruitment	✓	✓	✓						
Treatment procedures				✓	✓				
Evaluation					✓	✓			
Patients will be examined for caries activity and samples will be collected for microbiological assessment									
Data collection and statistical analysis						✓	✓		
Thesis submission								✓	✓

REFERENCES

1. Kassebaum, N. J. et al. Global, Regional, and National Prevalence, Incidence, and Disability-Adjusted Life Years for Oral Conditions for 195 Countries, 1990-2015: A Systematic Analysis for the Global Burden of Diseases, Injuries, and Risk Factors. *Journal of Dental Research* 96, 380–387 (2017).
2. Bernabe, E. et al. Global, Regional, and National Levels and Trends in Burden of Oral Conditions from 1990 to 2017: A Systematic Analysis for the Global Burden of Disease 2017 Study. *Journal of Dental Research* 99, 362–373 (2020).
3. Touger-Decker, R. & van Loveren, C. Sugars and dental caries. *The American journal of clinical nutrition* 78, (2003).
4. El Tantawi, M. et al. Prevalence and data availability of early childhood caries in 193 united nations countries, 2007–2017. *American Journal of Public Health* 108, 1066–1072 (2018).
5. Oubenyahya, H. & Bouhabba, N. General anesthesia in the management of early childhood caries: an overview. *Journal of Dental Anesthesia and Pain Medicine* 19, 313 (2019).
6. Milgrom, P. et al. Topical silver diamine fluoride for dental caries arrest in preschool children: A randomized controlled trial and microbiological analysis of caries associated microbes and resistance gene expression. *J Dent* 68, 72–78 (2018).
7. Gao, S. S. et al. Arresting early childhood caries using silver and fluoride products – A randomised trial. *Journal of Dentistry* 103, (2020).

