Appendix I

Table (1): ICDAS severity criteria³⁸

Score	Criteria
0	No change in enamel translucency with prolonged air drying
1	First visual change in enamel (after prolonged air drying)
2	Distinct visual change in enamel
3	Localized enamel breakdown or discolored enamel with no visible dentine involvement
4	Underlying dark shadow from dentine
5	Distinct cavity with visible dentine
6	Extensive distinct cavity with visible dentine

Table (2): ICDAS caries activity criteria³⁸

ICDAS code	Characteristics of Lesion	
	Active Lesion	Inactive Lesion
1, 2 or 3	Surface of enamel is whitish/yellowish opaque with loss of luster; feels rough when the tip of the probe is moved. Lesion is in a plaque stagnation area, i.e.: pits and fissures, near the gingival and approximal surface below the contact point.	Surface of enamel is whitish, brownish or black. Enamel may be shiny and feels hard and smooth when the tip of the probe is moved. For smooth surfaces, caries lesion is typically located at some distance from the gingival margin
4	Probably active	
5 or 6	Cavity feels soft or leathery on gently probing the dentin	Cavity may be shiny and feels hard on gently probing the dentin.

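### The washout rule names fluoride mouthwash but not professional fluoride varnish or gel, and reaches earlier SDF on a study lesion only indirectly

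*Combined protocol and SAP*

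**What the plan says.** The Exclusion criteria contain one rule on recent agents that could disturb the bacterial counts: "Reported usage of local or systemic antibiotics, chlorhexidine or fluoride mouthwashes within the last 2 weeks". Ascertainment is by report. No other section excludes, times or records earlier professional fluoride varnish or gel, and none names earlier SDF as a reason for exclusion.

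The study products belong to the classes left out. Under Materials, "Ten ml of 22,600 ppm of 5% Sodium fluoride varnish will be added to the nanosilver particles in a light proof brown bottle". Under Grouping, "Twenty-five children meeting the eligibility criteria will receive 38% Silver diamine fluoride". The Introduction states that "Silver diamine fluoride (SDF) has a proven antibacterial action".

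Two other criteria bear on the point. Inclusion requires "The presence of at least one active carious lesion on a primary tooth, with a score of 5", and Appendix I, Table 2 defines an active code 5 or 6 lesion by touch: "Cavity feels soft or leathery on gently probing the dentin". The Exclusion criteria also remove children with an obviously discoloured tooth, in an item otherwise about pain, pulpal infection, swelling and mobility. The Introduction and the Blinding section both say that SDF turns carious tissue black.

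The PICOT question under Study Design takes the percentage fall in lesion counts at one month as its outcome. The Statistical Analysis section gives sex, social status and diet as examples of confounders for regression. Prior topical treatment is not named there, and allocation is not stratified.

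**The concern.** The plan already accepts that recent topical fluoride is a reason to keep a child out, but it applies this only to mouthwash. Followed as written, a child who used a fluoride rinse last week is excluded, while a child who had varnish applied last week is admitted if a lesion still feels soft.

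The outcome is a change from the baseline sample. If earlier treatment has lowered that sample, or altered how the lesion responds, the child's result reflects the earlier exposure as well as the allocated product. The trial is small and keeps one spare child per arm (24 raised to 25), so it has little slack for avoidable noise. Recruitment is from a university paediatric dentistry clinic, where earlier professional fluoride is plausible, though the documents do not say how common it is.

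**Working it through.** **1. Which children the criteria catch.** This is a reading of the eligibility text.

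| Child at baseline | Washout rule | Active-lesion requirement | Discolouration item |
|---|---|---|---|
| Fluoride rinse one week ago | Excludes | – | – |
| Professional varnish one week ago, lesion still soft | Not named | Passes | No basis in the documents: the staining is ascribed to SDF |
| Earlier SDF, lesion still soft | Not named | Passes | May exclude, if the examiner counts a black lesion as a discoloured tooth |
| Earlier SDF, all lesions hard | Not named | Excludes | May exclude |

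The second row is uncovered. The third depends on how the examiner reads an item that is not written as a rule on prior treatment.

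**2. How it reaches the outcome.** Percentage fall = 100 × (baseline CFU − one-month CFU) / baseline CFU. Baseline enters both numerator and denominator. The activity check is tactile and gives no information on CFU, so it cannot show that a baseline count is already lowered.

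**3. Chance imbalance.** Inputs: 50 children, 25 per arm, no stratification (Sample size estimation; Randomization technique). The number exposed, K, is an assumption. With X exposed children in one arm, X is hypergeometric (50, K, 25), and the arms differ by 4 or more when |2X − K| ≥ 4.

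- K of 3 or fewer: impossible, probability 0.
- K = 4: 2·C(25,4)/C(50,4) = 2 × 12,650 / 230,300 = 0.11.
- K = 6: 2·[C(25,6) + 25·C(25,5)]/C(50,6) = 2 × (177,100 + 1,328,250) / 15,890,700 = 0.189.
- K = 10: X of 3 or fewer, or 7 or more, gives 0.289.

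These are probabilities of unequal numbers. They do not measure an effect on CFU.

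**4. Dilution.** The plan's 24 per group cannot be reproduced, because no effect size or SD is given. Solving backwards at two-sided 5% and 80% power (sidedness is not stated, so two-sided is assumed), the normal approximation gives d = (1.960 + 0.842) × √(2/24) = 0.81, and the t-test gives d = 0.83.

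Now suppose a share f of children, equal in both arms, shows no treatment difference at all, with the SD unchanged. The effect becomes d × (1 − f):

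| f (assumed) | Power at 24 per group | n per group for 80% |
|---|---|---|
| 0 | 80% | 24 |
| 5% | 76% | 27 |
| 10% | 71% | 30 |
| 20% | 61% | 37 |

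No treatment difference in any exposed child is the severe case; a partial loss would cost less. The documents give no value for f.

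**The case against.** The case on the other side is substantial, and most of it limits the point.

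- **Earlier SDF is partly covered.** The protocol says SDF blackens lesions and excludes obvious discolouration, so many children treated earlier could be turned away. This stands as far as it goes. The item does not say it is meant for prior silver treatment, and it does nothing about varnish.
- **Entry requires an active lesion.** A reader might infer that children enter with lesions already suppressed. The documents do not support that for clinical activity, since a child with only hard, arrested lesions cannot enter. What remains is a count that may be lowered without showing on probing.
- **Randomisation.** A reader might infer that lesions still soft after earlier SDF are non-responders to the control product and so tilt the trial against SDF. Such children go to both arms. A tilt would need non-response specific to SDF and not shared by a product that also combines silver and fluoride, and no section supports that.
- **One month.** A reader might infer that the rule contradicts the trial's own premise, because the Specific aims compare counts "after one month of the application of nanosilver fluoride or silver diamine fluoride". That is the follow-up time, not a statement that varnish alone lowers counts for a month. The Introduction ascribes the potent antimicrobial action to silver nanoparticles and says NSF's mechanism is unsettled.
- **Percentage scale.** A lower baseline does not by itself restrict a percentage fall unless counts approach the detection limit, which is not shown.
- **Open confounder list.** The regression could already include prior exposure. It could do so only if exposure is recorded, and the plan does not ask for that.

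**Conclusion.** The point holds as a cheap improvement. The washout omits professional fluoride varnish and gel, and deals with earlier SDF only through an item written for another purpose. The expected harm is dilution, extra variance and chance imbalance, not a demonstrated bias towards either arm.

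Its size cannot be stated. If no such children present, nothing is lost. At an assumed 6 to 10 of 50, an imbalance of 4 or more has a probability of 19% to 29%. At an assumed 5% to 20% with no treatment difference, power falls from 80% to between 76% and 61%. Both ranges rest on assumed shares, and the second also on an effect size solved backwards from the sample size. They show how sensitive a trial of 25 per arm would be, not what will happen.

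**What to change.** - Extend the exclusion criterion to (a) study lesions previously treated with SDF or another silver product, and (b) children with recent professional topical fluoride (varnish or gel). The investigators should justify the interval for (b); it should be no shorter than the two weeks already applied to fluoride mouthwash.
- Ascertain both by a caregiver question and a check of the clinic record, and record the answers at baseline.
- Adjust the between-group CFU comparison for baseline log CFU, separately for each organism. The baseline samples are already planned. This handles a lowered starting count; the exclusion and the record handle an altered response.
- If enrolment is complete, the clinic records can still support a sensitivity analysis without the exposed children.

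The cost is one screening question, one record check and one model term. The downside is that a few more screened children are deferred or turned away.

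### Participants are declared blinded, but the colour difference and black staining that rule out blinding the investigator are equally visible to the child and caregiver, and no masking is described

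*Combined protocol and SAP*

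**What the plan says.** The Blinding section first explains why the investigator is not blinded: "the SDF solution has a bluish tint and will stain the active caries lesions black". It describes the NSF liquid as yellowish and foresees no staining with it. The next sentence says that "the participants, the statistician, and the microbiologist will be blinded to the treatment group". Caregivers are not mentioned on either side.

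Under First visit: baseline examination, after consent has been obtained, the plan says: "The patients and caregivers will be informed about the therapeutic intervention to be applied, the possible outcomes, and side effects in detail". The same section adds: "All of the examinations and interventions will be done by one calibrated examiner". Under Allocation concealment, the envelope is held by an independent person "who will be assigned the role of opening it only at the time of intervention". The Harms/Risks item of the ethics section names "the risk of black discoloration with SDF treatment". Under Follow up: "All patients will be recalled after one month". The Study Design section commits the trial to CONSORT reporting.

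**The concern.** The plan treats a visible, arm-specific sign as enough to unblind one party and then declares another party, who carries that sign in the mouth for a month, to be blinded. No reason is given for the difference.

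Three things are at stake.

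- **Reporting.** A CONSORT report that repeats the statement would tell readers that bias from participants' knowledge of treatment was controlled by design. The plan's own description does not support that.
- **Home behaviour.** All families receive hygiene and diet advice, and the Statistical Analysis section names dietary habits as a potential confounder. The plan thus accepts that behaviour at home could affect the outcomes. Families who know or suspect the arm could behave differently during the month after randomisation. A blinded microbiologist protects the reading of the plates, not what happened in the mouth beforehand.
- **Recall.** Whether a child comes back at one month could also depend on what the family sees.

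**Working it through.** No arithmetic tests this point, and the sample size calculation does not bear on it. The check sets the relevant statements side by side.

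1. **Visible signs at treatment.** Both arms use one drop from a dappen dish, applied with a microbrush, with one minute on the lesion. The procedures look broadly alike, but the solutions are bluish and yellowish. Colour alone may mean little to a family that sees only one agent.

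2. **Visible signs afterwards.** Blackening is stated as a fact for SDF and is not expected for NSF. It lies on the treated lesion and can be seen between visits.

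3. **Masking measures.** The Blinding, Materials, Intervention and Follow up sections contain nothing that would hide the colour or the stain from the child or the adult present. The opaque envelope conceals the allocation until treatment. It does nothing after that.

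4. **What families know.** The first-visit sentence can be read in two ways.
   - If it refers to the agent this child will receive, the family knows the arm outright.
   - If it describes both agents in general, the family has been told the side effects in detail, and the one harm the ethics section names beyond standard care is blackening with SDF. A family given that information can infer the arm from the tooth.

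   Neither reading gives secure blinding beyond the treatment visit.

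5. **Who remains blinded.** The plan lists three parties. Removing participants leaves 3 − 1 = 2, the microbiologist and the statistician. Nothing in the stain argument touches these two.

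6. **Consequence for each outcome.** Colony counts are read by the blinded microbiologist. Caries activity is scored by probing, and one examiner does all examinations and interventions. That person handles the coloured solution and later sees the stained lesion. With participant blinding removed, caries activity has no blinding at treatment or at clinical assessment.

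7. **Margin for losses.** The Sample size estimation section raises 24 per group to 25, an allowance of 25 − 24 = 1 child, or 1/25 = 4%. The documents give no basis for predicting that losses will differ by arm, but there is little room if they do.

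**The case against.** The case on the other side has substance, and several parts of it stand.

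- **A reader might infer that caregivers are told which arm the child is in.** The documents do not say so. The sentence sits at the first visit, before the separate paragraph on the day of intervention, and the envelope is opened only at treatment. The timetable puts recruitment in months 1 to 3 and treatment in months 4 and 5. General information given before allocation is known is at least as natural a reading. Consent pages are not in the available text, so this cannot be settled here.
- **A reader might infer that nearly all 50 families would identify their arm.** That is not supported either. The plan does not say which teeth are treated or how visible the lesions are, and some families may not link a stain to an agent.
- **The blinding claim covers participants, who are aged 4 to 6, not caregivers.** This is correct, so the plan makes no false statement about caregivers. It is silent on the people who largely control hygiene, diet and attendance, and that silence is a gap to fill.
- **Families may react to black teeth whether or not they can name the arm.** This also stands. Part of the behavioural route is a consequence of the stain itself, and correcting the label does not close it. The correction changes what readers are told about it.
- **Neither outcome is reported by the participant, and the counts are read blind.** This limits the likely impact. The unblinded single examiner is probably the larger source of bias, and the plan already discloses that the investigator is unblinded.

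None of this restores the claim that participants are blinded.

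**Conclusion.** The point holds in a limited form. The plan states a design property, participant blinding, that its own description of the treatments gives no reason to expect, at least once staining appears. It also leaves caregivers' status unstated and is ambiguous on whether families are told the arm.

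The size is one of three blinding claims that should not be carried into the report. The documents give no figure for any effect on home behaviour, recall, bacterial counts or caries arrest, and none is asserted here. The conclusion rests on two assumptions: that the stain behaves as the plan describes, and that no masking measure exists beyond those written down. It does not depend on families being told the arm.

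A reader might go further and infer that the one-month comparison is biased. The documents support only that this route to bias is not closed in the way the plan says. The correction is worth making because it is specific, nearly free, and affects what readers may conclude about bias control.

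**What to change.** - **Blinding section.** Withdraw the statement that participants are blinded. State instead that the operator/examiner is unblinded, that participants and caregivers cannot be assumed blinded once staining appears, and that only the microbiologist and the statistician are blinded.
- **First visit: baseline examination.** State whether families are told the arm and, if so, when, so that the section agrees with the Blinding and Allocation concealment sections. A common information text on both agents is not pressed here: it may already be what the section intends, and it could make the arm easier to infer.
- **Report.** State that caries activity was scored by the unblinded examiner, with participants not assumed blinded, and that colony counts were read by a blinded microbiologist. This can still be done if enrolment is complete.

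The cost is wording in two sections and a less favourable blinding statement. Sample size, alpha, power, analysis and treatment do not change. The edit does not remove any behavioural effect of the stain; it stops the report from implying that such an effect was excluded.
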